### **Group A:**

: 8 patients indicated for lateral ridge augmentation in premolar-molar area (class I Seibert's classification) will be candidates to screw tent technique using single screw at crest position

### **Group B:**

8 patients indicated for lateral ridge augmentation in premolar-molar area (class I Seibert's classification) will be candidates to screw tent technique using double screws, one at a crestal position and the other one 5 mm apical to the first one.

## **Surgical Phase**

- All patients will receive prophylactic antibiotic (1 gm. Amoxicillin-clavulanate, Augmentin ®, GlaxoSmithKline, UK) one hour preoperatively and then every twelve hours for four days and will be instructed to rinse with 0.12% Chlorhexidine (Orovex ®, MACRO, Egypt) for one minute prior to surgery and twice daily for 2 weeks postoperatively.
- All procedures will be performed under local anesthesia utilizing articaine hydrochloride 4% with 1:100000 epinephrine (Septanest®, Septodont, USA).
- Sulcular incisions around teeth with mesial and distal vertical releasing incisions. A full thickness flap will be reflected on the buccal, and a full thickness flap will be reflected on the lingual/palatal to expose the residual alveolar ridge.
- Multiple cortical perforations will be performed with a 1/2 round bur to increase angiogenesis and supply of growth factors in all defect areas.
- In group A: single titanium bone screw will be placed in a crestal position to aid in graft stability. In group B: double titanium bone screws will be placed, one at a crestal position and the other one will be placed 5mm apical to the first one.
- In both groups the defect will be filled with allograft, the graft will be extended at least 10 to 12 mm in the apicocoronal direction.
- The grafted site will be covered with Bovine pericardium membrane
- Tension-free primary flap closure will be achieved and sutured using a 5-0 Polypropylene suture.
- 6 months later at the reentry, the bone screws will be removed and dental implant will be placed at the augmented site.

## **Postoperative instructions**

1. Routine verbal and written postoperative instructions for periodontal surgery will be given to all patients including ice compression on the surgical site during the first 4 h, a liquid and/or soft food diet for 3 days.
2. As with all surgical procedures, patients will be informed to contact our clinic if any problems will be developed during the postoperative period.
3. 1 gm. Amoxicillin-clavulanate (Augmentin ®, GlaxoSmithKline, UK) to be taken regularly every 12 hours for 4 days. Diclofenac Sodium 75 mg intramuscular injection (Voltaren, Novartis, Switzerland) was given every 12 hours for the first 48 hours and then was replaced with 50 mg enteric coated tablets taken only when needed. Patients were instructed to rinse with 0.12% Chlorohexidine 2 times per day for two weeks
4. The sutures will be removed after 2 weeks.
5. Patients were followed up for signs and symptoms of pain, inflammation, infection, wound dehiscence or membrane exposure 24 hours postoperatively, then day after day for the first week, and then monthly for 6 months.

## **Clinical assessment:**

At reentry 6 months later,

Keratinized mucosa will be measured using periodontal probe to the nearest millimeter

horizontal ridge width will be measured with a bone caliper to the nearest millimeter m at the midridge crestal level and then 5 mm apically. Same stent will be used for the standardization of the measurements

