## Aim of the study

**-First aim:** Evaluate the effectiveness of screw tent technique in horizontal ridge augmentation

**-Second aim:** Compare the effect of using single screw versus double screws on obtaining maximum bone gain.

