## Pre-surgical phase

- At the initial visit, each patient will receive a diagnostic work-up that included a full periodontal examination, standardized periapical radiographs and diagnostic study casts.
- Horizontal ridge width will be measured with a bone caliper to the nearest millimeter at the midridge crestal level and then 5 mm apically. Stent will be used for the standardization of the measurements.
- A preoperative cone-beam computed tomography (CBCT) will be performed for each patient who met the inclusion criteria before the surgery to determine bone height and width and to evaluate the underlying bone condition.
- These clinical and radiographic measurements will be repeated at reentry after 6 months of healing.

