## **Radiographic evaluation**

After 6 months CBCT imaging will be used to measure ridge width and bone density.

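### Caliper ridge width is read to the whole millimetre at both visits, adding rounding error of SD about 0.41 mm to a single-level gain; a 0.5 mm reading would recover most of the loss cheaply

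*Protocol*

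**What the plan says.** The section Aim of the study sets the comparison: "Compare the effect of using single screw versus double screws on obtaining maximum bone gain". The section Randomization puts 8 patients in each group.

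The reading rule appears twice. Pre-surgical phase states: "Horizontal ridge width will be measured with a bone caliper to the nearest millimeter at the midridge crestal level and then 5 mm apically". Clinical assessment repeats it for the 6-month reentry: "horizontal ridge width will be measured with a bone caliper to the nearest millimeter", at the same two levels. On positioning it adds: "Same stent will be used for the standardization of the measurements".

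There is also a radiographic measure of width. A CBCT is taken "before the surgery to determine bone height and width and to evaluate the underlying bone condition", and Pre-surgical phase adds: "These clinical and radiographic measurements will be repeated at reentry after 6 months of healing". Radiographic evaluation confirms: "After 6 months CBCT imaging will be used to measure ridge width and bone density". No reading resolution is given for CBCT, and the protocol does not say whether caliper or CBCT width carries the comparison of the two arms.

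**The concern.** A gain computed from the caliper can only be a whole number of millimetres at each level, because both readings are rounded to that unit. The stent fixes where the caliper is placed; it does not restore the fraction that is not recorded. The two sections agree with each other, so this is a choice of resolution and not a contradiction.

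Rounding acts in essentially the same way in both arms, so it should not bias the comparison. It does add noise, and with 8 patients per arm there is little precision to spare. The choice is made at data capture, so no later analysis plan can reverse it.

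The single-level figure matters here. The arms differ by a second screw 5 mm apical to the crestal one, and the lower caliper level is also 5 mm apical. That level is a natural place to look for a difference, and analysed alone it carries the full rounding error.

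**Working it through.** **Inputs from the protocol.** Reading unit h = 1 mm at both visits (Pre-surgical phase; Clinical assessment); two levels; 8 patients per arm (Randomization). The protocol states no SD, effect size, alpha, power, operator error or caliper graduation, so it has no figure of its own to reproduce.

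**Assumptions.** Two-sided 5% t-test; SD of the true gain between 0.5 and 2.0 mm; operator error of SD 0, 0.3 or 0.5 mm per reading; true difference set so that power would be 80% without rounding. With 8 per arm (noncentral t) that difference is 1.507 times the SD of the unrounded gain, operator error included.

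**Rounding error.**
- One reading: SD = h/√12. At 1 mm: 0.289 mm. At 0.5 mm: 0.144 mm.
- Gain at one level (two readings): variance = 2h²/12. At 1 mm: 0.167 mm², SD 0.408 mm. At 0.5 mm: 0.042 mm², SD 0.204 mm.
- Mean of the two levels: variance is halved. At 1 mm: 0.083 mm², SD 0.289 mm. At 0.5 mm: 0.021 mm².

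The finer reading removes 1 − 0.042/0.167 = 75% of the rounding variance and halves its SD. Simulation with 1,000,000 draws gave an error SD of 0.408 mm in four of five scenarios, and 0.387 mm where baseline widths varied with an SD of only 0.3 mm.

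**Power with a 1 mm / 0.5 mm reading** (80% without rounding):

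| SD of gain (mm) | One level, operator SD 0 | One level, operator SD 0.3 | One level, operator SD 0.5 | Two-level mean, operator SD 0 |
|---|---|---|---|---|
| 0.5 | 0.584 / 0.737 | 0.663 / 0.763 | 0.717 / 0.779 | 0.680 / 0.768 |
| 0.8 | 0.704 / 0.775 | 0.724 / 0.780 | 0.745 / 0.786 | 0.750 / 0.787 |
| 1.0 | 0.737 / 0.784 | 0.746 / 0.786 | 0.758 / 0.789 | 0.768 / 0.792 |
| 1.5 | 0.771 / 0.793 | 0.774 / 0.793 | 0.777 / 0.794 | 0.786 / 0.796 |
| 2.0 | 0.784 / 0.796 | 0.785 / 0.796 | 0.786 / 0.796 | 0.792 / 0.798 |

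The last column assumes that the gains at the two levels move together. A simulation of single-level trials (100,000 runs, baseline mean 4 mm and SD 1 mm) agreed within about 1 point: at SD 1.0 mm it gave 0.738 / 0.782, 0.748 / 0.787 and 0.758 / 0.790 for operator SD 0, 0.3 and 0.5 mm.

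**Information kept with a 1 mm reading at SD 1.0 mm.**
- One level, no operator error: 1/(1 + 0.167) = 86%, so about 1.1 of 8 patients per arm are lost.
- One level, operator SD 0.5 mm: the unrounded variance is 1 + 2 × 0.25 = 1.5, and 0.167/1.5 = 0.111; 1/1.111 = 90%, about 0.8 of 8 lost.
- Two-level mean, no operator error: 1/1.083 = 92%, about 0.6 of 8 lost.

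**Difference detectable with 80% power at SD 1.0 mm** (unrounded / 1 mm / 0.5 mm): 1.51 / 1.63 / 1.54 mm with no operator error; 1.85 / 1.95 / 1.87 mm with operator SD 0.5 mm.

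**The case against.** The strongest reply is that nothing in the protocol is wrong. The rule is disclosed and consistent, with the same unit, levels and stent at both visits, and it favours neither arm. What remains is a question of size, and the size rests on quantities the protocol does not give. The largest loss, about 21 points, needs an SD of gain of 0.5 mm, no operator error and one level analysed alone.

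Operator error could also exceed the range in the table. The baseline reading is taken in the pre-surgical phase and the second at reentry, and the protocol does not say whether the baseline reading is made over soft tissue. At SD of gain 1.0 mm, operator error of SD 0.75 mm gives power 0.770 / 0.793 for 1 mm / 0.5 mm readings; SD 1.0 mm gives 0.779 / 0.795. The recovery is then about 2 points. Even without operator error, the detectable difference falls by only 1.63 − 1.54 = 0.09 mm. CBCT width is outside the rule altogether. And if the caliper is marked in whole millimetres, a half-millimetre reading is an interpolation that may add error of its own.

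All of this limits the point, and it is why the point ranks as a minor improvement. It does not remove it: the benefit shrinks under larger operator error but stays positive, the caliper data are collected in any case, and the lost fraction cannot be restored later.

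**Conclusion.** The concern holds as a low-priority point of design. The 0.41 mm rounding SD follows directly from the stated rule, provided ridge widths vary enough between patients for rounding errors to be spread evenly. The effect on power depends on the assumed SD of gain:

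- **SD about 1.0 mm, one level:** a loss of about 6, 5 or 4 points for operator SD 0, 0.3 or 0.5 mm. The finer reading recovers about 4 to 5, 4 and 3 of them. With the two levels averaged and no operator error, about 3 are lost and 2 recovered.
- **SD 1.5 mm or more:** a loss of 3 points or fewer, with about 2 or fewer recovered.
- **SD 0.5 mm:** the loss becomes material, about 21 points without operator error, or about 8 with operator SD 0.5 mm, of which about 6 are recovered.

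Recovering most of the loss is true of variance and power; the rounding SD itself is only halved. The conclusion applies to the caliper gain alone. If CBCT width carries the comparison, the cost of this rule is zero.

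**What to change.** Before baseline readings are taken, amend the caliper resolution in Pre-surgical phase and in Clinical assessment. Ridge width should be recorded to the nearest 0.5 mm, or finer where the caliper's graduation allows, with the same graduation for every patient, visit and level. The change concerns caliper ridge width only; the keratinized mucosa reading stays as it is.

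The cost is one phrase in two sections and possibly a finer-graduated caliper. It needs no extra patients, visits or procedures. The benefit is limited by the instrument's graduation and repeatability, neither of which the protocol states, and the change does not make up for 8 patients per arm.

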## **Radiographic evaluation**

After 6 months CBCT imaging will be used to measure ridge width and bone density.

## **Statistical analysis:**

-All data will be tabulated and analyzed by statistical method.

